5.4 End of study

The earliest data cut-off for the primary analysis of ORR may take place 3 months after the last patient enrolled, to allow all patients to complete two follow-up RECIST assessments. At this time, DoR and safety/tolerability will also be summarized. The CSR of primary analysis may include, but not limited to, ORR, DoR, safety and tolerability data.

The full CSR of Part B will report the analysis of all primary and secondary endpoints (including updated ORR and DoR, DCR, tumor shrinkage, PFS and OS). The data cut-off for this analysis will take place approximately 8 months after the last patient is enrolled to ensure that the last responder could be followed up for at least 6 months after initial documented response. All patients will continue to be followed up for an updated analysis based on cut-off that will occur between 12 - 24 months after the last patient is enrolled. All endpoints will be updated and summarized in an addendum to the CSR. The study may be terminated at individual centers if the study procedures are not being performed according to GCP, or if recruitment is slow. Dizal may also terminate the entire study permaturely if concerns for safety arise within this study or in any other study with DZD9008.

Date: July 24,2023

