4. PATIENT SELECTION AND RESTRICTIONS

Investigators should keep a record, e.g, patient screening log, of patients who entered pre-study screening. Eligibility should be reviewed and documented by the investigator, or appropriately qualified delegate, prior to enrolment.

Each patient must meet all of the inclusion criteria (core inclusion criteria and cohort specific criteria) and none of the exclusion criteria at the time of starting study treatment. Under no circumstances there can be exceptions to this rule.

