6.8 Anti-tumor efficacy

6.8.1 Tumor assessments

6.8.1.1 Imaging assessment

RECIST 1.1 criteria will be used to assess tumor response to treatment by determining Objective Response rate (ORR), Disease Control Rate (DCR), Duration of Response (DOR) and Progression Free Survival (PFS). The RECIST 1.1 guidelines for measurable, non-measurable, target and non-target lesions and the objective tumor response criteria (complete response, partial response, stable disease or progression of disease) will be used for the assessment of tumors according to Appendix F.

Imaging assessments will be performed using CT scan or MRI to assess extracranial lesions, such as chest, abdomen (including liver and adrenal glands). MRI is the preferred method for analyzing the brain lesion if brain metastasis presents at baseline (within 28 days of treatments start, ideally as close as possible to the start of study treatment), on Cycle 3 Day 1 (\pm 7 days) and then every 6 weeks \pm 7 days until objective disease progression or withdrawal from study. Contrast-enhanced CT can be used if MRI is not feasible. In addition, additional areas should be investigated based on the signs and symptoms of the patient. Any other sites at which new disease is suspected should also be appropriately imaged. If an unscheduled assessment is performed and the patient has not progressed, every attempt should be made to perform the subsequent assessments at their scheduled visits.

Categorization of objective tumor response assessment will be based on the RECIST 1.1: CR (complete response), PR (partial response), SD (stable disease) and PD (progression of disease). Target lesion (TL) progression will be calculated in comparison to when the tumor burden is at a minimum (i.e. smallest sum of diameters previously recorded on study). In the absence of progression, tumor response (CR, PR, SD) will be calculated in comparison to the baseline

Date: July 24,2023

tumor measurements obtained before starting treatment. For objective response rate (ORR), a visit response of CR or PR must be confirmed by a later scan conducted at the next scheduled visit and no less than 4 weeks after the initial visit response of CR or PR.

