The full CSR of Part B will report the analysis of all primary and secondary endpoints (including updated ORR and DoR, DCR, tumor shrinkage, PFS and OS). The data cut-off for this analysis will take place approximately 8 months after the last patient is enrolled to ensure that the last responder could be followed up for at least 6 months after initial documented response. All patients will continue to be followed up for an updated analysis based on cut-off that will occur between 12 - 24 months after the last patient is enrolled. All endpoints will be updated and summarized in an addendum to the CSR.

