3.4 Full Analysis Set (FAS)

The Full Analysis Set (FAS) will consist of all NSCLC patients with documented EGFR Exon20ins mutations in tumor tissue, who were previously treated with platinum-based chemotherapy, received at least 1 dose of DZD9008 and have measurable disease at baseline as identified by IRC. The mutation in tumor tissue (resection, biopsy, pleural effusion pellet processed in formalin-fixed paraffin-embedded block, etc.) will be determined based on the clinical trial assay. The patients wrongly reported as EGFR Exon20ins mutations by local lab will be excluded from FAS, such as the complex mutation

FAS is the primary set for efficacy analysis. Patients will be analyzed according to their initially assigned dose level in FAS.

To support the development and approval of companion diagnosis devices, two additional analysis sets were defined in CSP as subset of FAS:

Centrally Confirmed EGFR Exon20ins by Tumor Tissue Analysis Set

All patients in FAS with EGFR Exon20ins mutation confirmed in tumor tissue by central laboratory.

• Centrally Confirmed EGFR Exon20ins by Plasma ctDNA Analysis Set

All patients in FAS with EGFR Exon20ins mutation confirmed in plasma ctDNA by central laboratory.

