When confirmation of CR/PR is required, BOR of CR or PR will only be claimed if a response of CR/PR is recorded by two visits with time interval of at least 4 weeks (28 days). For confirmed CR, one intervening response of NE are possible and are acceptable, but PD is not; For confirmed PR, one intervening response of NE or SD are possible and are acceptable, but PD is not. More examples for BOR derivation with confirmation required are provided in Table 1. Note the BOR variable provided by IRC will not be used for statistical analysis directly, as new anticancer therapy was not considered in the derivation rule by IRC.

BOR where confirmation of response is required or not will be derived and reported respectively. Eventually ORR will be calculated based on the BOR derived for each patient, as defined above.

Table 1 Derivation of BOR where confirmation is required

			1
Assessment x	Assessment x+1	Assessment x+2	BOR
Death			NE (for death before the first RECIST assessment)
CR	CR	CR/PD/NE	CR
CR	NE	CR	CR
PR	CR	CR	CR
PR	CR	PD/NE	PR
PR	PR	Any	PR
PR	SD/NE	PR	PR
CR	PR		Not allowed. Reappearance is progression
CR	PD/NE		SD*
PR	SD/PD/NE		SD*
SD/NE	CR	PD/NE	SD*
SD/NE	PR	SD/PD/NE	SD*
SD	PD		SD*
PD			PD
NE			NE
NE	PD		PD
NE	NE		NE

^{*} SD is believed to be the best overall response only if the minimum time requirement (5 weeks from baseline) for SD is met.

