5.6.1 Primary Efficacy Analysis

The primary endpoint for Part B of study is ORR according to RECIST 1.1 by IRC, where confirmation of response is required. The definition and derivation of ORR can be found in Section 4.2.1.

• 300 mg

P value for the test against the null hypothesis of ORR will reported based on the Simon's two-stage method. ORR and two-sided 97.5% CI will be calculated based on Jung's method [4] to adjust the bias caused by optional sampling in the Simon's two-stage design. Jung's method will provide the uniformly minimum variance unbiased estimator of ORR and CI based on binomial distribution.

• 200 mg

P value in this cohort will be calculated based on binomial exact test and the 97.5% CI of ORR will be calculated using the exact (Clopper - Pearson) method. These statistics will be considered as descriptive.

The number (%) of patients with best overall response will also be provided in the following categories: CR, PR, SD, PD and NE.

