5.6.2.5 ORR by Investigators

ORR assessed by investigators will be analyzed in FAS using the same analysis method described in Section 5.6.1. But the p value and confidence interval reported will only be considered as descriptive.

5.6.2.6 **OS**

The definition and derivation of OS can be found in Section 4.2.2.6.

Overall survival will be analyzed in FAS. The number (%) of patients with event (death) or censored before data cut-off will be summarized. Breakdown of censors (alive at the end of study, lost to follow-up and etc) may also be summarized.

The overall survival rates (at 3, 6, 9 and 12 months and etc) and quartiles of OS will be estimated for each treatment group based on Kaplan-Meier method. OS data will also be displayed graphically using a Kaplan-Meier plot.

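### The earliest permitted cut-off for confirmed ORR leaves the last-enrolled patients without the scan that would confirm a response first seen at scan 2

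*Protocol*

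**What the plan says.** - **Cut-off.** Protocol 5.4 and SAP 2.2 use the same sentence: the earliest cut-off for the primary ORR analysis "may take place 3 months after the last patient enrolled, to allow all patients to complete two follow-up RECIST assessments". A full report follows at about 8 months after the last patient is enrolled, "including updated ORR and DoR, DCR, tumor shrinkage, PFS and OS". A further update comes at 12-24 months.
- **Scans.** SAP 2.2 starts tumour assessments at Cycle 3 Day 1 (±7 days) and repeats them every 6 weeks (±7 days).
- **Confirmation.** SAP 4.2.1 requires confirmed response: "BOR of CR or PR will only be claimed if a response of CR/PR is recorded by two visits", at least 28 days apart. Protocol 6.8.1.1 is tighter: a first CR or PR "must be confirmed by a later scan conducted at the next scheduled visit and no less than 4 weeks after" that first response.
- **Denominator.** Under SAP 3.4 the FAS takes patients with the documented mutation and prior platinum who "received at least 1 dose of DZD9008 and have measurable disease at baseline as identified by IRC". It sets no minimum follow-up.
- **Meaning of enrolled.** Protocol 4 says "Eligibility should be reviewed and documented by the investigator, or appropriately qualified delegate, prior to enrolment", which places enrolment after the eligibility review. Protocol 6.3.1 ties enrolment to the giving of consent, and screening may take up to 28 days before first dose.

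**The concern.** The reason given for 3 months is that every patient will have had two follow-up scans. That is enough for unconfirmed response. For confirmed response, the second scan can only confirm a response already seen at the first. A patient near the end of accrual whose tumour first meets PR at scan 2 has an open result at the cut-off. That patient is scored as a non-responder because the confirming scan has not yet been taken.

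SAP 2.2 attaches the primary analysis to this cut-off. At stake are some power against the final boundary, and a primary ORR and 97.5% CI that sit slightly low until the 8-month update.

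**Working it through.** **Inputs**
- Day 1 is first dose (SAP 7.1); a month is 30.4375 days (SAP 4.1).
- Scans fall 42, 84 and 126 days after first dose, each ±7 days (SAP 2.2).
- Per-arm design: stop at 7 or fewer responses in 39 (Protocol 5.3.3); N = 103 and expected ORR 0.30 (SAP 2.4); null ORR 0.17 (Protocol 7.9.7.1); one-sided level 0.0125 (Protocol 7.2.2, SAP 2.4).

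**Step 1: the plan's own figure.** 3 × 30.4375 = 91.3 days. Scan 2 at its latest is 84 + 7 = 91 days. So 3 months does just cover two scans, if enrolment and first dose coincide. The floor is about study Day 92.

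**Step 2: when a scan-2 response is confirmed.** On schedule this is scan 3, 126 days after first dose (Day 127), window 119-133 days (Days 120-134). The gap after the floor date is:
- nominal: 126 − 91.3 = 34.7 days (5.0 weeks)
- window: 119 − 91.3 = 27.7 days to 133 − 91.3 = 41.7 days (4.0 to 6.0 weeks)

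Patients first dosed in about the last 4-6 weeks of accrual are therefore affected. Earlier patients have already had scan 3.

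**Step 3: if enrolled means consent.** First dose may come 28 days later. The floor is then 91.3 − 28 = 63.3 days after first dose, before scan 2 even at its earliest (77 days). On that reading two scans may not fit.

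**Step 4: design check.** In an exact two-stage binomial calculation (continue if more than 7 of 39), the smallest final count that keeps the level at or below 0.0125 is 27 of 103. It gives alpha 0.0111 and power 80.1%; a count of 26 gives alpha 0.0196. The final count is not visible in the documents, so 27 is derived.

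**Step 5: size, by assumption.** The documents give neither accrual rate nor time to response. Assume 103 patients over 12-24 months, which is 1.97 to 0.99 a week. Then 4 weeks × 0.99 ≈ 4 and 6 weeks × 1.97 ≈ 12 patients are pending, all in stage 2. Each has counted-response probability 0.30 × (1 − late fraction), where the late fraction is the share of responders first responding at scan 2. The final count is the convolution of stage 1, the non-pending stage-2 patients and the pending patients. The ORR shortfall is pending × 0.30 × late fraction / 103.

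| Pending | Late 10% | Late 20% | Late 30% | Late 40% |
|---|---|---|---|---|
| 4 | 79.6% | 79.0% | 78.4% | 77.8% |
| 6 | 79.3% | 78.4% | 77.4% | 76.5% |
| 12 | 78.4% | 76.4% | 74.4% | 72.2% |

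The entries are power, against 80.1% with none pending. The shortfall in ORR runs from 4 × 0.30 × 0.10 / 103 = 0.12 points to 12 × 0.30 × 0.40 / 103 = 1.40 points. In the middle case (6 pending, 20-30% late) it is 0.35-0.52 points, or 0.36-0.54 missed responders. Alpha with 12 pending and 40% late is 0.0061, below 0.0111.

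**The case against.** **It is only a floor.** The sentence sets the earliest date at which the sponsor may cut, and a later cut-off already complies. This stands: the bias arises only if the floor is used. A reader might infer that the plan contradicts its own endpoint. It does not; it permits a date that serves the endpoint poorly for the last patients.

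**The updates recover it.** This also stands. Eight months is 243.5 days, well past scan 3 at its latest (133 days), even if 28 days of screening are taken off.

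**The effect is small and rests on guesses.** Largely right. The middle case loses about half a responder. Other guesses move the figure: 20 pending with 40% late would give 65.5% power, but nothing in the documents points to that. Only the calendar arithmetic is certain.

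**An unscheduled scan could confirm sooner.** The SAP's 28-day rule alone would allow Day 113 from a nominal scan 2, or Day 106 from an early one. Both are after Day 92, no such scan is scheduled, and Protocol 6.8.1.1 asks for the next scheduled visit.

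**Any cut-off leaves something pending.** True, and the remedy shares this limit. But a third scan gives every patient the scheduled confirmation of a scan-2 response, which two scans cannot.

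A reader might also infer that repeated ORR looks inflate type I error. They do not. With N fixed, the same critical count and no re-reads, confirmed responders can only accumulate, so a rejection at any cut-off implies rejection at the last.

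Finally, a reader might infer that the confirmatory result is undefined, because SAP 5.6.1 names no cut-off while SAP 5.6.2.5 says of investigator ORR "But the p value and confidence interval reported will only be considered as descriptive". The documents do not support that. Calling the first look primary and the later ones updated already implies which look carries the test. An explicit label is missing detail.

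**Conclusion.** The point holds as a cheap improvement. The timing gap follows from the documents' own schedule and is certain. Used at its floor, the cut-off falls about 5 weeks (4-6 with visit windows) before scheduled confirmation of a scan-2 response in the last patient.

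The consequence is modest: with 4-12 pending patients, 10-40% late responders and a true ORR of 30%, power is between 79.6% and 72.2% instead of 80.1% (middle case about 77-78%), and ORR is about 0.1-1.4 points low. The direction is against the drug. It does not mean that scan-2 responses in general go unconfirmed; only the last few weeks of accrual are affected. The gap widens if enrolment is read as consent.

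**What to change.** In SAP 2.2, set the primary ORR cut-off no earlier than 133 days (18 weeks plus the 7-day window; 133 / 30.4375 = about 4.4 months) after the last patient's first dose. Every FAS patient can then have a third scheduled scan, and counting from first dose removes the ambiguity in enrolled. The protocol already allows a later date, so the SAP alone can set this, and Protocol 5.4 can be aligned at its next amendment.

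The cost is that the earliest read-out moves about 6 weeks (133 against 91 days). That is still about 110 days before the 8-month cut-off (243.5 − 133) when enrolment and first dose coincide. Two groups stay unconfirmed until the update: responses first seen at scan 3, and scan-2 PRs followed by one SD or NE, which SAP Table 1 lets a later PR confirm. Both would be confirmed at scan 4 (Day 169).

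Optionally, add a line to SAP 5.6.1 that ORR, CI and p value at later cut-offs are descriptive.

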5.5 Post study access to study treatment

Any patients still receiving investigational product at the time of end of the study will be able to continue to receive DZD9008 if in the opinion of investigator they continue deriving clinical benefit with agreement with Dizal study physician. Re-consent is required. Such patients will continue to be monitored for safety assessments until DZD9008 is discontinued. These patients will then be followed up for treatment-related Serious Adverse Events up to 28 days after the last dose of investigational product. A CSR addendum will be prepared to summarize any additional safety data collected.

6. STUDY PLAN AND COLLECTION OF STUDY VARIABLES

6.1 Study plan

Descriptions of the procedures are included in Table 11, Table 12, Table 13 Table 14. The schedule of assessments may change in response to emerging data, updated assessment tables will be provided outside of the protocol. All study visits from Cycle 2 Day 1 onwards may be performed within a visit window of \pm 2 days.

6.2 Recording of data

Web Based Data Capture (WBDC) will be used for data collection on the observations, tests and assessments specified in the protocol and query handling. The investigator will ensure that data are recorded on the CRFs as specified in the protocol and in accordance with the instructions provided.

The investigator will ensure the accuracy, completeness, and timeliness of the data recorded and for the provision of answers to data queries according to the Clinical Study Agreement or applicable information.

The investigator will sign the completed CRFs. A copy of the completed CRFs will be archived at the study site.

For details of data and study management, see Appendix E of this Clinical Study Protocol.

6.3 Safety assessment

6.3.1 Enrolment and screening

At enrollment, each potential patient will provide informed consent prior to starting any study specific procedures (see Appendix D of this Clinical Study Protocol for Ethics and Regulatory Requirements).

IRT system will be used in this study to assign patient enrollment code. Each potential patient will be assigned an unique enrollment number. If a patient withdraws from the study, then the enrollment code cannot be reused.

Demographic data and other characteristics will be recorded and will include date of birth or age, gender, race and/or ethnicity according to local regulations, and smoking history.

Edition Number: 12. Date: July 24,2023

A standard medical, medication and surgical history will be obtained with review of the selection criteria with the patient.

Each patient will undergo screening (Table 11, Table 12, Table 13, Table 14) during the 28 days prior to first dosing to confirm eligibility. Screen failure reason needs to be recorded in EDC system. Tumor assessment and other clinical data obtained as standard of care prior to consent may be used for the study provided the assessments fall within the protocol specified period prior to the first dose of study drug.

All patients should have brain MRI or contrast-enhanced CT within 28 days of first dose to exclude leptomeningeal metastasis or active brain metastasis.

Prior to discharge from each in-patient and clinic visit, the Investigator or their deputy will be responsible for reviewing all available data including vital signs and ECG tracings.

Subjects who have failed previous screening are permitted to be re-screened for once. ICF should be re-signed, and an updated subject code will be assigned. Screening procedures must be repeated (unless the study procedures meet the time window requirement for the second screening). If subjects have provided tumor tissues and/or plasma samples for EGFR Exon20ins mutation confirmation, then no additional tumor tissue and/or plasma samples need to be provided at the re-screening.

6.3.2 Physical examination

A physical examination will be performed and include an assessment of the followings: general appearance, skin, head and neck (including ears, eyes, nose and throat), respiratory, cardiovascular, abdomen, lymph nodes, thyroid, musculo-skeletal (including spine and extremities) and neurological systems. Performance status will be assessed at the visits as indicated in the Study Plan according to ECOG criteria as follows:

- 0 = Fully active, able to carry out all pre-disease activities without restrictions
- 1 = Restricted in physically strenuous activity but ambulatory and able to carry out work of a light or sedentary nature e.g., light housework, office work
- 2 = Ambulatory and capable of self-care, but unable to carry out any work activities. Up and about more than 50% of waking hours
- 3 = Capable of only limited self-care, confined to bed or chair more than 50% of waking Hours
- 4 = Completely disabled, cannot carry on self-care, totally confined to bed or chair

6.3.3 Vital sign

Blood pressure and pulse rate

Blood pressure and pulse rate will be measured in supine or siting position after 10 minutes rest. Assessments will be performed at the visits as shown in the Study Plan (Table 11, Table 12, Table 13, Table 14). Observations will be recorded at the following times:

Clinical Study Protocol Drug Substance: DZD9008 Protocol No.: DZ2019E0001

Edition Number: 12.0 Date: July 24,2023

Part A

- Screening
- First dosing day (Cycle 0 Day 1) for dose escalation: pre-dose, 1, 2, 4, 6, 10 and 24 hours post-dosing
- On day 1 and day 9 of food effect cohort in Part A: pre-dose, 1, 2, 4, 6, 10 and 24 hours post-dosing (treatment time might be updated upon emerging human PK data).
- First day of multiple dosing (Cycle 1 Day 1): pre-dose, 1, 2, 4, 6, 10 and 24 hours post-dosing
- Cycle 1 Day 8 and 15: pre-dose, 1, 2, 4, 6, 10 and 24 hours post-dosing
- On Day 1 of each subsequent cycles: one assessment at any time during day
- On occurrence of any cardiac AE or clinically indicated at the discretion of the investigator
- Discontinuation visit

Part B

- Screening
- Cycle 1 Day 1, Cycle 1 Day 8 and Cycle 1 Day 15: Pre-dose
- On Day 1 of each subsequent cycles: one assessment at any time during the day
- On occurrence of any cardiac AE or clinically indicated at the discretion of the investigator
- Discontinuation visit
- The timing and frequency of vital signs assessment may be adjusted in response to emerging PK and safety data.

Weight

Weight will be assessed at screening and then Day 1 of each cycle and at the discontinuation visit.

Height

Height will be assessed at screening only.

Any changes in vital signs should be recorded as an AE if applicable.

Date: July 24,2023

